Title page:

Title: Comparison of Clinical and Radiographic Success Between:
Mineral Trioxide Aggregate (MTA) & Ferric Sulfate (FS) Pulpotomies for Primary
Molars.

NCT 02783911

Date: Sep 02, 2014

Statement of Problem

Premature loss of a tooth from caries or trauma can lead to malocclusion and/or to esthetic, phonetic, function problems, super eruption of the opposing tooth and costly procedures to correct and maintain space. A pulpotomy is one type of treatment for vital pulp therapy. The aim of the treatment is to preserve the radicular pulp, avoiding pain and swelling, to retain the tooth and preserve arch integrity.

Formocresol (FC) has a long history for pulpal medicament with a success rate of up to 97%. Its use, however, has been questioned due to published studies raising concerns for systemic distribution, carcinogenicity, mutagenicity, and immune sensitization. These concerns have led to the search and use of different materials and techniques to replace FC as a pulpal medicament that is cost effective, safe, and predictable. Calcium hydroxide, diluted formocresol, electrosurgery, lasers, ferric sulfate (FS), mineral trioxide aggregate (MTA), and sodium hypochlorite have been used as alternatives to FC for pulp therapy. Of these alternatives, MTA and FS have the most similar clinical and radiographic success as FC but the number of studies evaluating their success is limited in primary teeth. There has not been any study comparing MTA to FS for use in primary molar pulpotomies.

The purpose of this study is to evaluate which of these materials, gray MTA (GMTA) or FS, has the best long-term success rates with the least amount of adverse effects in primary molar pulpotomies. We will clinically and radiographically compare the success rates of MTA and ferric sulfate pulpotomies in primary teeth.

Review of Literature

- 1) Pulpotomy is still the most common treatment for cariously exposed pulps in symptom-free primary molars. The aim of this treatment is to preserve the radicular pulp, avoiding pain and swelling, and ultimately to retain tooth and thus preserve arch integrity. The desired end result is the timely exfoliation of the treated tooth and its replacement by a permanent successor. The procedure can be briefly described: following removal of coronal ceiling of the pulp, the coronal pulp is amputated using either a sharp excavator or a slowly revolving large round bur. A pulp dressing agent is applied and a base of zinc oxide-eugenol (ZOE), either plain or reinforced, is placed over amputation site, immediately followed by a final restoration, preferably a stainless-crown. (Fuks, A.B., 2012)
- 2) Formocresol (FC) has been a popular pulpotomy medicament in the primary dentition for the past 60 years, and is considered the most universally taught and preferred pulp therapy for primary teeth (Eidelman, E., 2001).
- 3) Concerns have been raised about the toxicity and potential carcinogenicity of FC in humans, and alternatives have been proposed to maintain partial pulp vitality (Eidelman, E., 2001).

- 4) A 2008 survey detected a trend away from the teaching of 1:5 diluted formocresol, with more using ferric sulfate for pulpotomy (Casamassimo, P. S., 2013)
- 5) Ferric Sulfate is proposed as a pulpotomy agent on the theory that its mechanism of controlling hemorrhage might minimize the chances for inflammation and internal resorption believed by some investigators to be associated with physiological clot (Smith, N.L., 2000)
- 6) The most frequently observed pulpal responses were calcific metamorphosis and internal resorption. Sometimes (n=5) both responses were observed in the same tooth (Smith, N.L.,2000)
- 7) Clinically,86.6% success rate was found in ferric sulfate group whereas 100% success rate was found in electrosurgical and diode laser groups (Yadav, P., 2014)
- 8) MTA has many desirable properties such as biocompatibility, alkaline pH, radiopacity, excellent sealing capacity, the ability to harden in presence of humidity, the formation of dentin, cement, and bone (Chen, J.W., 2012)
- 9) MTA is a biocompatible material and its sealing ability is better than that of amalgam or zinc oxide-eugenol. It is a powder that sets in the presence of moisture with a pH of 12.5. The setting time of the cement is 4 hours and its compressive strength is 70 MPA, which is comparable with that of IRM (Torabinejad, M., 1999).

Methods and Materials

Children between the ages of 4-9, with first or second primary molars with normal or reversible pulpitis that have vital carious pulp exposures due to caries and pulps that bleed when entering the pulp chamber. No clinical symptoms or evidence of pulp degeneration, such as excessive bleeding from the root canal, history of swelling, mobility, or sinus tract. No radiographic signs of internal or external root resorption, inter-radicular and/or periapical bone destruction, or furcation radiolucency. No more than one third physiologic root resorption has occurred. Teeth that will be retained for 12 months after the pulpotomy procedure and stainless steel crown restoration, will be asked to participate in this study. Children can be ASA I or II that have cooperative behavior that will enable follow-up appointments for examinations and radiographs. Children meeting the criteria for this study will be treated at Loma Linda University's Pediatric Dental Clinic, LLU Children's Hospital with general anesthesia, or Koppel Special Care Dentistry Center at LLU.

Prior to pulpotomy treatment, the subjects will be randomly assigned into two groups: 1) MTA pulpotomy with stainless steel crown or 2) ferric sulfate with stainless steel crown. Operators involved will draw blindly into a box that has 60 papers: 30 marked MTA and 30 marked FS. The teeth will be anesthetized using 2% lidocaine with (1:100Kepi). The tooth will be isolated using a rubber dam. A new slow-speed #6 or #8 round bur will be used to remove caries. A new #330 carbide bur and a high speed will be used to access pulp chamber. Hemostasis will be achieved with direct pressure from a sterile cotton pellet moistened with sterile water. MTA or FS (whichever randomly assigned) will be placed onto pulpal stumps. ZOE B&T mixture will be placed into pulp

chambers. Molar will be immediately restored with a stainless steel crown cemented with Ketac-Cem Liquid. A post procedure bitewing radiograph, that shows the subject's tooth furcation and complete root, will be taken.

Follow-up appointments at 6 months, 9 months, and 12 months will be completed for subjects. The follow-up appointments will consist of a clinical examination and bite-wing view periapical radiographs to determine success(s)/failure(s) of two different pulpotomized teeth.

The criteria for a successful pulpotomy will include:

- retained for the length of the study or exfoliate naturally
- normal bone trabeculation in the periapical region
- no abscess or fistula
- contained internal resorption is acceptable
- calcific metamorphosis is acceptable

When the teeth exfoliate or require extraction, the teeth with pulpotomies will be collected and histologic slices will be completed to analyze for what types if any cellular changes from the use of the pulpal medicaments.

Statistical Analysis:

Data and statistical analysis will include descriptive and inferential statistics. Inferential statistical analysis will use SPSS 16 (SPSS, Chicago, IL) with a significance level set at $P \leq 0.05$

Budget:

Item	Units Needed	Price/Unit	Total Price
Patient incentive – follow-up visits	60	\$50	\$3000
Mineral Trioxide Aggregate	5 dose packets	\$475	\$475
Ferric Sulfate	1	\$35	\$35
3M Stainless steel crowns	60	\$5	\$300
Copying, stationery , paper, pen, 2 clip board			\$300.00
Total			\$4,110

Proposed Research Milestones:

Continuation of Established IRB#: 5140262

March 2016:

- Data collection

March 2016:

- Proposal preparation and submission for approval by the Research Guidance Committee

April 2016:

- Protocol preparation, submission, and approval by Loma Linda University School of Dentistry Research Committee

June 2016- June 2017:

- Data analysis and article preparation for review and submission

References:

- Casamassimo, P. S. (2013). Pediatric Dentistry Infancy Through Adolescence. St. Louis, Missouri, Elsevier Saunders.
- Chen, J. W. (2012). "Materials for primary tooth pulp treatment: the present and the future." Endodontic Topics 2012 **23**: 41-49.

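### As written, the operator draws the arm before opening the tooth, although two entry criteria can be judged only after pulp access, and there is no rule for a tooth that then fails them

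*Protocol*

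**What the plan says.** All of the relevant text is in the Protocol, Methods and Materials.

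- **Timing of allocation:** "Prior to pulpotomy treatment, the subjects will be randomly assigned into two groups".
- **Method of allocation:** "Operators involved will draw blindly into a box that has 60 papers: 30 marked MTA and 30 marked FS".
- **Steps listed after the draw:** local anaesthesia, rubber dam, caries removal, then access ("A new #330 carbide bur and a high speed will be used to access pulp chamber"), haemostasis with a moistened cotton pellet, and finally "MTA or FS (whichever randomly assigned) will be placed onto pulpal stumps".
- **Entry criteria that concern bleeding:** the tooth must have "vital carious pulp exposures due to caries and pulps that bleed when entering the pulp chamber", and there must be no "evidence of pulp degeneration, such as excessive bleeding from the root canal". No threshold is given for what counts as excessive.
- **A sentence suggesting that eligibility comes first:** "Children meeting the criteria for this study will be treated at" the named clinics.

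Neither the Protocol nor the SAP has a second eligibility check before the draw, a rule for a tooth found ineligible after it, a rule for that tooth's slip, or a definition of the analysis set.

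**The concern.** Randomisation makes the arms comparable only if the decision to include a tooth does not depend on its assignment. Here the last part of that decision falls after the operator has seen the slip. Drawing blindly means that the slip is picked unseen; it does not hide the arm once the slip is in hand.

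The judgement most exposed is whether root canal bleeding is excessive, because it is discretionary. If operators apply it more strictly in one arm, teeth with a poorer outlook leave that arm and stay in the other. The comparison of success rates is then biased. A larger sample would not remove that bias, and exclusions that were never logged cannot be recovered by later analysis.

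**Working it through.** **1. When each criterion can be observed.**

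| Step, in the Protocol's order | Arm known to operator? | Criterion first observable |
|---|---|---|
| Slip drawn | yes, from here on | none of the two |
| Anaesthesia, rubber dam, caries removal | yes | none of the two |
| Pulp chamber opened | yes | bleeding on entry; excessive root canal bleeding |
| Haemostasis | yes | – |
| Material placed | yes | arm first needed here |

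Two is a conservative count, since a vital carious exposure may itself be confirmed only during caries removal. The listed steps before placement are the same in both arms, so nothing in the procedure requires the arm to be known earlier.

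**2. How often the missing rule would be needed.** The documents give no rate of failure at access. If a share f of teeth failed there, the chance of at least one in 60 draws is 1 − (1 − f)^60. At f = 5% this is 1 − 0.95^60 = 0.95, with 60 × 0.95 = 57 eligible teeth expected. At f = 20% it exceeds 0.99, with 60 × 0.80 = 48 expected.

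**3. Size of a possible bias.** The plan has no figure to reproduce, and every rate here is an assumption. Let s be the share of opened teeth that are borderline, b their failure rate, 10% the failure rate of the rest, and d the share of borderline teeth excluded in one arm only. That arm's failure rate is

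F(d) = [s(1 − d)b + (1 − s) × 0.10] / [s(1 − d) + (1 − s)].

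| s | b | F(0) | F(0.5) | F(1) | Shift, half excluded | Shift, all excluded |
|---|---|---|---|---|---|---|
| 0.10 | 0.30 | 0.120 | 0.105/0.95 = 0.1105 | 0.100 | 0.9 points | 2.0 points |
| 0.20 | 0.30 | 0.140 | 0.110/0.90 = 0.1222 | 0.100 | 1.8 | 4.0 |
| 0.10 | 0.50 | 0.140 | 0.115/0.95 = 0.1211 | 0.100 | 1.9 | 4.0 |
| 0.20 | 0.50 | 0.180 | 0.130/0.90 = 0.1444 | 0.100 | 3.6 | 8.0 |

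**4. Scale against sampling error.** SE = √[p(1 − p)(1/n1 + 1/n2)], with p = F(0) in both arms.

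The SAP does not state the arm sizes, but its chi-square footnote restricts them. The minimum expected count of 2.25 times 24 cases gives 54 as the product of the smaller row total and the smaller column total. Both are at most 12, so they must be 6 and 9. The margins are 6/18 and 9/15, and the documents do not say which is the arm.

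| p | 30 v 30 | 9 v 15 | 6 v 18 |
|---|---|---|---|
| 0.12 | 8.4 points | 13.7 | 15.3 |
| 0.14 | 9.0 | 14.6 | 16.4 |
| 0.18 | 9.9 | 16.2 | 18.1 |

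At 24 cases, half exclusion gives from 0.95/15.3 = 0.06 to 3.56/16.2 = 0.22 SE. Full exclusion gives from 2.0/15.3 = 0.13 to 8.0/16.2 = 0.49 SE. At the planned 30 per arm the ranges are 0.95/8.4 = 0.11 to 3.56/9.9 = 0.36, and 2.0/8.4 = 0.24 to 8.0/9.9 = 0.81.

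**The case against.** **The order is not certain.** The draw sentence carries no time of its own. The order rests on the phrase placing assignment before treatment and on the sequence of the text. Item 1 of the Review of Literature begins its account with removal of the pulp chamber roof, but does not settle when a pulpotomy starts. The sentence about children who meet the criteria shows an intention to settle eligibility first. This stands as a caveat. It does not answer the point, because nothing in either document puts the draw after access, and these two criteria cannot be settled before it.

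**A reader might infer that the bias favours MTA.** Item 5 of the Review of Literature says "Ferric Sulfate is proposed as a pulpotomy agent on the theory that its mechanism of controlling hemorrhage might minimize the chances for inflammation", which could make an operator holding an FS slip readier to keep a bleeding tooth. The documents do not support that direction. Haemostasis is by moistened cotton pellet in both arms before either material is placed, so FS is not the Protocol's means of stopping bleeding. Item 5 goes on to internal resorption, so it is a theory of pulpal response and not a reason for selecting teeth. Items 8 and 9 describe MTA as hardening or setting in moisture, so an operator holding an MTA slip might be equally relaxed about a wet field.

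**Only one criterion is truly discretionary.** Whether the pulp bleeds at all leaves little room for judgement. This stands: the exposure lies mainly in the word excessive.

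**The result is already reported.** The SAP gives a final chi-square table, so a change in timing cannot help those teeth. This also stands, and it limits what can be done for them to reporting.

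**Conclusion.** The point holds as a weakness in the written design: the operator can know the arm at the last eligibility judgement, and no rule covers a tooth that fails it. It opens a route to selection bias, of unknown direction, that is cheap to close.

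A reader might take the fall from 60 slips to 24 analysed cases as a sign that teeth were dropped after the draw. It is not evidence of that, since incomplete enrolment or loss to follow-up would give the same count. The documents contain no evidence that exclusion differed by arm.

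The plausible size is modest: 0.9 to 3.6 points for half exclusion and 2.0 to 8.0 points as an upper bound, below half a standard error at 24 cases. These figures assume 10% to 20% borderline teeth failing at 30% to 50%, other teeth failing at 10%, exclusion in one arm only, and independent cases. They illustrate scale and do not estimate what occurred.

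**What to change.** **In the Protocol, Methods and Materials.** State that the slip is drawn, or its content revealed, only after the existing access-dependent criteria have been checked and immediately before the material is placed. Add or change no clinical criterion. Log every draw, and analyse every tooth drawn after that point in its assigned arm. The box of 60 slips can stay as it is. If practice already followed this order, one sentence saying so settles the matter.

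**Cost.** Two or three sentences and a draw log. The practical downside is that both materials must be ready and the slip is drawn or opened mid-procedure, with the rubber dam in place and sometimes under general anaesthesia.

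**For teeth already treated.** The timing cannot be changed. Report by arm the slips drawn, teeth excluded after the draw with reasons, teeth lost to follow-up and teeth analysed, as far as records allow, and state the limitation. The cost is one table.

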Title page:

Title: Comparison of Clinical and Radiographic Success Between:
Mineral Trioxide Aggregate (MTA) & Ferric Sulfate (FS) Pulpotomies for Primary Molars.

NCT 02783911

Date: Sep 02, 2014

Comparison of Mineral Trioxide Aggregate and Ferric Sulfate:
Pulpal Medicaments for Pulpotomized Primary Teeth

Statistical analysis plan

The following clinical information were collected from the charts: Mobility, pain, abscess/draining fistula, and facial swelling. Exfoliation of the pulp treated teeth was recorded and graded as normal, early, or delayed based on the age of the patient at the time of the recall and on the exfoliation status of the contralateral tooth. If there is any clinical signs of the above the tooth will be count as clinical failure.

Data was analyzed using the Statistical Package for Social Sciences v 16.0 (SPSS Inc., Chicago, Ill). The difference between the materials was analyzed using chi-square, Significance level was set $P < .05$.

Chi-Square Tests

	Value	df	Asymptotic Significance (2- sided)	Exact Sig. (2- sided)	Exact Sig. (1- sided)
Pearson Chi-Square	.059 ^a	1	.808		
Continuity Correction ^b	.000	1	1.000		
Likelihood Ratio	.060	1	.807		
Fisher's Exact Test				1.000	.603
Linear-by-Linear Association	.057	1	.812		
N of Valid Cases	24				

a. 2 cells (50.0%) have expected count less than 5. The minimum expected count is 2.25.

b. Computed only for a 2x2 table

Summary: The result showed there is no statistical difference in long term clinical success between the two pulpotomy medicaments. (MTA vs FS)

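### The treating operators draw their own assignments from a single box of slips, and no step described commits them to the slip drawn or records it.

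*Protocol*

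**What the plan says.** The protocol (Methods and Materials) places assignment before treatment and makes the child the unit: "Prior to pulpotomy treatment, the subjects will be randomly assigned into two groups". The mechanism is one sentence: "Operators involved will draw blindly into a box that has 60 papers: 30 marked MTA and 30 marked FS". The paragraph then goes through the operative steps, including "MTA or FS (whichever randomly assigned) will be placed onto pulpal stumps", so whoever places the material must know the arm. Children are treated in three places: the university's paediatric dental clinic, "LLU Children's Hospital with general anesthesia, or Koppel Special Care Dentistry Center at LLU".

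Neither document mentions numbered or sealed slips, a holder of the box, a record of each draw, a rule against returning a slip, or stratification by setting.

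The SAP says "The difference between the materials was analyzed using chi-square". It ties the clinical signs to the charts but does not say where the arm was read from, or whether teeth were grouped by assignment or by material received. Its table shows 24 against "N of Valid Cases" and notes "The minimum expected count is 2.25". It gives no arm sizes and no breakdown by setting.

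**The concern.** Random allocation protects the comparison only if the first slip stands. Concealment has two parts: the operator must not know the next assignment, and must not be able to undo it once seen. A blind draw from a box meets the first. Nothing described meets the second. The person reading the slip is, on the natural reading, the person about to treat the tooth, who has already seen the child and the preoperative radiographs. If that person thinks one material suits the tooth better, putting the slip back takes a moment and leaves no evidence.

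The effect would be to sort harder teeth into one arm, in a trial where randomisation is the only protection described against such sorting. Without a log, nobody could later check whether it happened, how many slips were drawn, or whether each tooth received the material on its slip.

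**Working it through.** **1. The plan's own figure.** The SAP gives no arm sizes, but its table can be rebuilt. In a 2x2 table with N = 24, the minimum expected count is the product of the two smaller margins divided by N, so the product is 2.25 × 24 = 54. With both margins at most 12, only 6 × 9 fits. The margins are 6/18 and 9/15. The cells [[2, 4], [7, 11]] give

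Pearson = 24 × (2×11 − 4×7)² / (6×18×9×15) = 864 / 14,580 = 0.059, p = .808,

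which matches the SAP. The likelihood ratio (.060), linear-by-linear (.057) and Fisher values (1.000 and .603) also match, and no other table with these margins does. The analysed arms are therefore 9:15 or 6:18; the table does not show which margin is the arm.

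**2. Does the split point to redrawing?** If the 24 were simply 24 draws from a 30/30 box, the two-sided hypergeometric probability of a split at least this uneven is .187 for 9:15 and .003 for 6:18. The first is compatible with chance. The second would not be, but the documents do not say whether the other 36 slips were never drawn or the teeth were lost or excluded. The split is not evidence of redrawing.

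**3. Size of a redraw bias.** All inputs are assumptions; the documents give none:
- half the teeth are high-risk, failing at 40%, and the rest fail at 10%;
- the materials do not differ;
- a fraction r of high-risk teeth that draw MTA is redrawn once, with an even chance at the second draw.

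A high-risk tooth then ends in MTA with probability 0.5(1 − r) + 0.25r = 0.5 − 0.25r. A low-risk tooth does so with probability 0.5.

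| r | High-risk teeth going to MTA | MTA failure | FS failure | Difference |
|---|---|---|---|---|
| 0.2 | 0.450 | (0.225×0.4 + 0.25×0.1)/0.475 = 24.2% | (0.275×0.4 + 0.25×0.1)/0.525 = 25.7% | 1.5 points |
| 0.5 | 0.375 | (0.1875×0.4 + 0.25×0.1)/0.4375 = 22.9% | (0.3125×0.4 + 0.25×0.1)/0.5625 = 26.7% | 3.8 points |

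If operators preferred the other material for difficult teeth, the sign reverses.

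**4. Against sampling error.** At 25% failure the standard error of the difference is √(0.25×0.75×(1/9 + 1/15)) = 18.3 points at 9 v 15, and √(0.25×0.75×(2/30)) = 11.2 points at 30 v 30. The modelled bias is well inside both.

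**The case against.** **The draw is blind and comes before the pulpotomy.** As written, the operator cannot see the next slip and has not yet seen the exposed pulp, which limits how well teeth could be sorted by risk. This stands as a limit on size. It does not close the gap, because the look of the tooth and the child is already known.

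**Silence is not absence.** This stands. The documents do not say that no log was kept or that slips were returned; they describe no safeguard.

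**The modelled bias is small and assumed.** This also stands. The SAP reports p = .808 and claims no advantage for either material.

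Two stronger readings are tempting.

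- *A reader might infer that the SAP groups teeth by the material received, as read from charts.* The SAP attributes only the clinical signs to charts. It leaves the grouping rule unstated, and no switch of material is documented.
- *A reader might infer that one box serving three settings, with 24 cases analysed, confounds material with setting.* Suppose half the sample is in one setting (assumed). A between-arm gap of 20 points or more in that share then has probability 20% at 30 v 30, 22% at 12 v 12, 40% at 9 v 15 and 64% at 6 v 18. The last figure rests on the less plausible split and on a coarse grid: with 12 of 24 in the setting, the only possible gaps are 0, 22, 44 and 67 points, so any departure from balance counts. Over three settings of assumed sizes, the chance that the largest gap reaches 20 points does rise, from 24–35% with 60 to 51–57% with 24. But chance imbalance under random allocation is not bias, and the test's error rate allows for it. No outcome rates by setting are given, so an imbalance cannot be turned into an effect.

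**Conclusion.** The concern holds as a weakness of allocation concealment. The protocol states a concrete method that lets the treating operator read a slip before anything commits that slip to a child, and a better method is almost free. The change should be made, but it does not overturn the reported result.

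The illustrative bias is 1.5 to 3.8 percentage points. It rests wholly on the assumed risks, risk mix and redraw rates, and on a consistent preference among operators. Unlike sampling error, it would not shrink with more teeth. The documents do not support a claim that redrawing occurred, that teeth were analysed by material received, or that setting confounds the comparison.

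**What to change.** **Protocol.** Replace the box with 60 sequentially numbered, opaque, sealed envelopes (30 MTA, 30 FS) in random order, prepared by a team member who does not treat study teeth. The operator takes the next envelope, writes child, tooth and date on it, and only then opens it. The used envelopes are the allocation log.

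**SAP.** State that groups are compared by the arm in the envelope. Report how many teeth received the other material. Tabulate assignments and analysed teeth by arm and setting, descriptively; 24 cases over three settings are too sparse for more.

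**Stratification by setting is optional.** Operators know each material they place, so small blocks let them work out late assignments. With m slips per arm, the expected number of forced final assignments is 2m/(m + 1): 1.9 of 60 in a single sequence, but 1.3 of every 4, or 1.5 of every 6, when the block size is known. If stratification is used, block sizes should vary and be withheld from operators. It would not correct imbalance from later loss.

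**Cost.** Preparing 60 envelopes should take about an hour (an estimate), with no extra staff or visits. A single sequence must be reachable from all three settings, as one box would be. Stratifying would need a separate set at each.

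**Teeth already treated.** The SAP already reports results, so envelopes cannot help that cohort. What remains is to say who held the box and whether slips were returned, report slips drawn by arm and setting where recorded, account for the path from 60 to 24, and analyse by slip drawn.

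### The SAP fixes no assessment time for clinical failure, so teeth watched for different periods can be counted alike, and its long-term conclusion goes beyond the 12-month visit schedule

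*Protocol*

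**What the plan says.** **Protocol**

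- Statement of Problem: the purpose is to find which material "has the best long-term success rates with the least amount of adverse effects in primary molar pulpotomies". No duration is attached.
- Methods and Materials, eligibility: "Teeth that will be retained for 12 months after the pulpotomy procedure and stainless steel crown restoration".
- Methods and Materials, follow-up: "Follow-up appointments at 6 months, 9 months, and 12 months will be completed for subjects". No later visit is scheduled, and none of the three is named as the endpoint.
- Methods and Materials, success criteria: the only one that refers to time is "retained for the length of the study or exfoliate naturally". It names no month.

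**SAP**

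- Data source: "The following clinical information were collected from the charts: Mobility, pain, abscess/draining fistula, and facial swelling".
- Failure rule: "If there is any clinical signs of the above the tooth will be count as clinical failure".
- Only reference to time: exfoliation is graded "based on the age of the patient at the time of the recall". The recall is undated.
- Analysis: one chi-square between materials, with 24 valid cases.
- Summary: "The result showed there is no statistical difference in long term clinical success between the two pulpotomy medicaments".

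The SAP gives no visit, window, minimum follow-up, censoring rule or rule for missed visits. Neither document says what long term means.

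**The concern.** Under the SAP rule, success is simply the absence of a charted sign. That depends on how long the tooth was watched as well as on how it fared, because cumulative failure can only rise with time. Nothing in the SAP keeps a tooth last examined clean at 6 months from counting on equal terms with one examined clean at 12.

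Two things are at stake. First, the failure proportion has no defined time, so it cannot be read as a 12-month risk. If the mix of follow-up differed between arms, the comparison could show a difference that the materials did not cause, or hide one that they did. Second, the only reported conclusion is about long-term success, while the visits that are meant to supply the evidence end at 12 months.

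**Working it through.** **1. Reproduce the SAP table.** Inputs from the SAP output: N = 24, minimum expected count 2.25, two cells with expected count below 5, Pearson chi-square .059.

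- The minimum expected count is the product of the two smaller margins divided by N, so that product is 2.25 × 24 = 54. Each smaller margin is at most 12, and only 6 and 9 multiply to 54. The margins are therefore 9/15 by 6/18.
- Expected counts: 6×9/24 = 2.25; 6×15/24 = 3.75; 18×9/24 = 6.75; 18×15/24 = 11.25. Two are below 5, as printed.
- With an observed 2 in the smallest cell, every cell differs from expectation by 0.25. Chi-square = 0.0625 × (1/2.25 + 1/3.75 + 1/6.75 + 1/11.25) = 0.0593, p = 0.808.
- The table [[2, 7], [4, 11]] also returns the other printed results: continuity-corrected .000, likelihood ratio .060, Fisher 1.000 and .603, linear-by-linear .057.

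The arithmetic is correct. The output does not show which margin is the treatment arm or which outcome level is failure. It does show one binary outcome per case and no time dimension.

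**2. Cases analysed against cases planned.** The protocol's box holds 60 slips, 30 per material. 24/60 = 40%. The documents do not explain the gap.

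**3. What an undefined assessment time could do (illustration).** The documents give no visit-level data, so two assumptions are needed: a constant hazard, and a true 12-month failure risk F12 of 10% to 40%.

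- Failure seen by month t: F(t) = 1 − (1 − F12)^(t/12).
- If half the teeth in both arms are last seen at 6 months and half at 12, the pooled reading is 0.5 × F12 + 0.5 × F(6).

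| True F12 | Seen by 6 months | Pooled, half last seen at 6 months |
|---|---|---|
| 10% | 5.1% | 7.6% |
| 25% | 13.4% | 19.2% |
| 40% | 22.5% | 31.3% |

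At 25%, pooling reads 5.8 points low, in both arms alike.

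**4. Would removing the early-seen clean teeth cure it?** Take 100 teeth with F12 = 25%, half unobserved after 6 months for reasons unrelated to outcome.

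- Failures seen: 50 × 0.25 + 50 × 0.134 = 12.5 + 6.7 = 19.2.
- Teeth kept if early failures stay and early-seen clean teeth are dropped: 50 + 6.7 = 56.7.
- Apparent failure: 19.2/56.7 = 33.9%, which is 8.9 points too high.

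Dropping them errs by more than pooling does.

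**5. Using each tooth's observed time.** Same 100 teeth.

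- Failure by 6 months is 13.4%.
- Of the half still followed, 50 − 6.7 = 43.3 are clean at 6 months, and 12.5 − 6.7 = 5.8 of these fail by 12 months: 5.8/43.3 = 13.4%.
- Twelve-month failure = 1 − (1 − 0.134)² = 25%, the true value.

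Without the assumption that loss is unrelated to outcome, the bounds are 19.2% (all 43.3 unseen clean teeth succeed) and 19.2% + 43.3% = 62.5% (all fail).

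**The case against.** The strongest reply is that the protocol does set a time criterion, "retained for the length of the study or exfoliate naturally", after three visits that are all meant to take place. On a natural reading, a tooth last seen at 6 months has not been shown to meet it, and the SAP does not withdraw it. This stands in part. The criterion limits what can be charged, but it names no month and concerns retention rather than the last clean examination. The SAP's failure rule does not restate it.

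A second reply is that pooling of recall times is inferred. This stands. A reader might take 24 cases out of 60 slips as proof of short follow-up, or conclude that success is overstated in both arms. The documents support neither. The gap fits under-recruitment, or exclusion of teeth without a final visit, just as well.

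Third, the analysed data may run past 12 months. The protocol plans to collect teeth at exfoliation or extraction, the SAP grades exfoliation as normal, early or delayed, and the protocol's milestones place data collection in March 2016 for a document dated September 2014. This also stands: relabelling the result as 12-month without checking the charts could be wrong. It does not rescue the analysis, because longer undated recalls would also leave assessment time unfixed.

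Finally, a reader might infer a difference between arms of about 12 points (25% − 13.4% = 11.6). That needs one whole arm seen only to 6 months and the other wholly to 12, and nothing in the documents suggests it.

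**Conclusion.** The point holds as a defect in how the outcome is defined and how the conclusion is worded. Followed as written, the SAP lets teeth with different observation times count equally, and the scheduled visits do not support a long-term claim. This is more than missing detail, because the trial's only reported conclusion rests on it.

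The documents do not establish that any of the 24 cases was last seen early, that follow-up differed between arms, or how large any bias is. The fall from 25% to about 19% is an illustration. It rests on a constant hazard, an assumed true risk, and half the teeth in both arms last seen at 6 months. Because it affects both arms alike, it concerns the level of failure and is not evidence of a false difference between materials. The printed chi-square is arithmetically sound and is not in question.

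**What to change.** In the SAP:

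- Name the scheduled 12-month visit as the primary assessment time, with a window, and restate the protocol's retention criterion with that date attached.
- Tabulate for each arm, at 6, 9 and 12 months, the teeth examined, failed, exfoliated naturally and not seen.
- Estimate 12-month failure with a time-to-event or interval-censored method that censors each tooth at its last clean examination, and say how natural exfoliation enters, since the protocol treats it as success. Alternatively, give best-case and worst-case bounds for teeth not seen at 12 months. Do not count those teeth as successes or drop them from the denominator.
- Report actual follow-up duration by arm.
- In the Summary, replace the long-term wording with the actual duration: 12 months if the recalls followed the schedule, otherwise whatever the charts show.

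The cost is SAP wording, re-tabulation of chart data already held, and slightly more analysis work. The estimates will be less certain and the claim more modest. The censored estimate assumes that loss to follow-up is unrelated to outcome; the bounds do not, but with 24 cases they may be wide.
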